##### Premedication with Systemic Steroids

- **Lead-In part.** Subjects should not receive premedication with systemic steroids, with the following exceptions:
  - In the event that a subject experiences an **infusion reaction** (i.e. within 24 hours of infusion) CTCAE grade 2 or 3 after the first administration of E7777 on Cycle 1 Day 1, the premedication regimen for that subject must be supplemented during the rest of Cycle 1 (Days 2-5) with systemic corticosteroids (see below). Steroid premedication may be administered during subsequent treatment cycles at the discretion of the treating physician
  - In the event that a subject experiences an infusion related reaction at any time during any treatment cycle, the premedication regimen for that subject may be supplemented with systemic corticosteroids during the remainder of treatment days for that cycle (if event occurred before completion of cycle treatment) and/or in subsequent treatment cycles, at the discretion of the treating physician
  - Systemic corticosteroid premedication should be dexamethasone 4 mg, slow intravenous push OR equivalent corticosteroid dose according institutional guidance.
- **Main Study.** Same guidance as for the Lead-In part.

#### 9.4.1.2 Drug Preparation and Administration

##### **Frozen Drug Formulation (Lead-In only)**

The instructions below should be followed for preparation and administration of the frozen formulation of E7777 which is used in the Lead-In part:

- Thaw vials in the refrigerator at 2 to 8 °C (36 to 46 °F) for not more than 24 hours or at room temperature for 1 to 2 hours.
- Bring E7777 to room temperature, before dose preparation.
- Mix the solution in the vial by gentle swirling; do not shake.
- Visually inspect for particulate matter and discoloration prior to administration, whenever solution and container permit. Use only if the solution is clear, colorless, and without visible particulate matter. After thawing, a haze may be visible which should clear when the solution is at room temperature.
- Do **not** refreeze E7777 after thawing.
- Prepare and hold diluted E7777 in plastic syringes or soft plastic i.v. bags. Do **not** use glass containers.
- Maintain concentration of E7777 at 15 µg/mL or higher during all steps in the preparation of the solution for i.v. infusion.
- Withdraw the calculated dose from the vial(s) and inject it into an empty i.v. infusion bag. Do not add more than 9 mL of sterile saline without preservative to the i.v. bag for each 1 mL of E7777.
- Do **not** administer as bolus injection.
- Do **not** mix E7777 with other drugs.
- Do **not** administer E7777 through an in-line filter.

- Administer prepared solutions of E7777 within 6 hours, using a syringe pump or i.v. infusion bag.
- Discard unused portions of E7777 immediately.

### **Lyophilized Drug Formulation (Main Study only)**

The instructions below should be followed for preparation and administration of the lyophilized formulation of E7777 which is used in the Main Study only:

- E7777 is reconstituted with 2.1 mL of sterile Water for Injection prior to administration.
- Mix the solution in the vial by gentle swirling; do not shake.
- Visually inspect all the vials reconstituted for particulate matter and discoloration prior to administration. Use only if the solution is clear, colorless, and without visible particulate matter. After reconstitution, a haze may be visible which should clear when the solution is allowed to stand for a while at room temperature.
- Prepare and hold diluted E7777 in plastic syringes or soft plastic (except for polystyrene) i.v. bags. Do **not** use glass containers.
- Maintain concentration of E7777 at 15 µg/mL or higher during all steps in the preparation of the solution for i.v. infusion.
- Withdraw the calculated dose from the vial(s) and inject it into an empty i.v. infusion bag. Do not add more than 9 mL of sterile saline without preservative to the i.v. bag for each 1 mL of E7777.
- Do **not** administer as bolus injection.
- Do **not** mix E7777 with other drugs.
- Do **not** administer E7777 through an in-line filter.
- Administer prepared solutions of E7777 within 6 hours, using a syringe pump or i.v. infusion bag.
- Discard unused portions of E7777 immediately.

#### 9.4.1.3 Monitoring Procedures During Administration

Prior to administering E7777:

- Ensure the facility is equipped and staffed for cardiopulmonary resuscitation.
- Monitor vital signs.

- Monitor the following protocol-specified tests to ensure criteria for treatment are met: liver function tests, complete blood count (CBC), albumin, creatine phosphokinase (CPK), and renal function (Day 1 only).
- Assess neurological status prior to each infusion including memory, orientation, gait, and numbness in extremities.
- Monitor body weight prior to each infusion.
- Monitor blood pressure.
- Perform medical exploration specifically addressed to detect early signs of peripheral edema.

During administration of E7777, monitor as follows:

- Ensure epinephrine (0.1 to 0.5 mL of 1:1000 solution subcutaneous), diphenhydramine (50-mg i.v. push), and methylprednisolone sodium succinate (250-mg/mL i.v. push) or other medical preparation per local institutional guidelines for the treatment of infusion reactions are at the bedside.
- Monitor for allergic reaction.
- Perform frequent respiratory assessments.
- Monitor vital signs before and at the end of the infusion and at 30 minutes postinfusion.

General recommendations for administration of E7777 are: to minimize the risk or to reduce the intensity of acute infusion-related reactions (e.g., fever, chills, tachycardia, etc.) that may occur, the infusion may be slowed or stopped temporarily until symptoms resolve. Withhold E7777 treatment if serum albumin levels are  $< 3.0$  g/dL (CTCAE Grade  $\geq 2$ ) or if clear signs of CLS occur e.g. peripheral edema, with or without functional impairment, cardiopulmonary impairment, or hypotension. CPK testing is required if CLS is suspected and it should be monitored frequently as clinically indicated until resolution of CLS.

#### 9.4.1.4 Management of Acute Infusion Reaction and Hypersensitivity During Administration

The administration of E7777 should be withheld if the subject develops any of the following:

- Diastolic pressure below 60 mmHg or above 100 mmHg
- Pulse rate faster than 130 beats per minute (bpm)
- Shaking chills, rigors
- Oral temperature higher than 39.4 °C

- Respiratory distress

Administration of E7777 can be resumed if the subject's signs and symptoms return to baseline; E7777 administration will be withheld for that day if the condition does not resolve.

In the event a hypersensitivity reaction occurs, the following medications should be readily available during each administration:

- Diphenhydramine (50-mg i.v. push) or other antihistamine per local institutional guideline for hives, itching, rash, shortness of breath, and/or chills
- Methylprednisolone sodium succinate (250-mg/mL i.v. push) or per local institutional guideline for decrease in blood pressure (BP) and/or respiratory distress
- Epinephrine 0.1 to 0.5 mL of a 1:1000 solution subcutaneous for anaphylaxis
- Prochlorperazine (10-mg i.v. push) or institutional antiemetic agent of choice. Subjects may receive antiemetics, as needed, for the control of nausea and/or vomiting

#### 9.4.1.5 Dose Interruption or Modification

##### **Dose Delays**

- Dose delays will be allowed for toxicities. Resumption of dosing will be according to the guidelines provided in [Table 1](#).
- The maximum delay is 21 days before the day the next course is scheduled to start.
  - A full dose will be given if toxicities are resolved within this 21-day period.
  - A dose delay lasting > 21 days will lead to permanent discontinuation of treatment.
  - If a cycle is not delivered in full, regardless of the reason, the missing doses will not be replaced and the cycle will be considered as complete. The missing doses will be captured per dose intensity calculations.
- Two consecutive dose delays due to toxicity will lead to a permanent dose reduction by 50% without possible reescalation.
  - Only one dose reduction to 50% will be allowed, regardless of the reason. The requirement for additional dose reductions, as defined previously, will lead to permanent discontinuation of treatment.
- The starting date of a new cycle will coincide with the date of treatment resumption following a dose delay or dose reduction.
- Dose delays are also allowed for scheduling purposes and if in the subject's best interest in the opinion of the investigator. The maximum delay for this is 42 days.

Study drug interruption and dose reduction instructions for subjects who experience an E7777-related toxicity are presented in [Table 1](#).

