## 9.4 Treatments

### 9.4.1 Treatments Administered

E7777 will be administered by intravenous (i.v.) infusion over 60 minutes ( $\pm$  10 minutes) on 5 consecutive days in every 21-day cycle.

The E7777 dose in the Lead-In will be as assigned by CRM.

The E7777 dose in the Main Study will be 9  $\mu$ g/kg.

Treatment will stop upon completion of 8 cycles or disease progression\* or unacceptable toxicity. Subjects who have attained skin tumor response and are deriving clinical benefit from E7777 treatment may continue receiving treatment beyond 8 cycles, at the discretion of the treating physician.

The investigator or subject may also stop study treatment at any time for safety or personal reasons; however subject should remain on study, if possible, for follow-up.

\*Treatment may continue after first notation of disease progression (PD) if the investigator

is of the opinion that PD needs to be confirmed, eg, in cases where (a) the apparent increased tumor burden in the skin or lymph nodes may reflect immune reaction/flare, or (b) the subject shows improvement or stable disease in the skin but increase in lymph node size. In this case, treatment will stop after 2 successive notations of PD.

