**Table 1 Dose Interruption and Modification During Treatment Period**

Toxicity	Dose Interruption	Dose Modification
Capillary leak syndrome a Grade 4	Discontinue study treatment permanently	N/A
Capillary leak syndrome Grade 3, 2. assessed as dose-limiting , e.g. severe symptoms requiring hospitalization for acute intervention	Interrupt dosing until resolved to ≤ Grade 1	Resume at 50% dose
Capillary leak syndrome Grade 3, - assessed as not dose-limiting , e.g. less severe symptoms leading to hospitalization for prophylactic treatment with fluids or diuretics	Interrupt dosing until resolved to ≤ Grade 1	Resume at full dose
Infusion reaction b Grade 4 or Recurrent infusion reaction Grade 3 that recurs despite premedication with systemic steroids	Discontinue study treatment permanently	N/A
Infusion reaction Grade 2 or 3, first occurrence	None	Continue at full dose, but add systemic steroid premedication
Recurrent infusion reaction Grade 2 that recurs despite premedication with systemic steroids	Interrupt dosing until resolved to ≤ Grade 1	Resume at full dose, but may add systemic steroid premedication f
Infusion related reaction c Grade 2 or 3	Interrupt dosing until resolved to ≤ Grade 1	Resume at full dose, but may add systemic steroid premedication f
Visual loss d	Discontinue study treatment permanently	N/A
Grade ≥ 3 hematological ≥ 7 days, or febrile neutropenia, or bleeding. Exception: Grade 3 lymphopenia e	Interrupt dosing until toxicity ≤ Grade 1, or until clinical symptoms are resolved	No change; Resume at full dose
Grade 3 nonhematologic toxicity except nausea, vomiting, or elevation of liver enzymes.	Interrupt dosing until toxicity ≤ Grade 1 or baseline	No change; Resume at full dose
Grade 4 nonhematologic toxicity other than, nausea, and vomiting.	Discontinue study treatment permanently	N/A

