6.7.1 Extent of Exposure

The number of cycles/infusions on treatment, quantity of study drug administered, and duration of study drug treatment will be presented. The number of subjects requiring dose reductions, treatment interruption will be summarized.

- The number of cycles received and the number of infusions by cycle and overall will be summarized with descriptive statistics. Subject is considered to have received one cycle if the subject received at least one dose on any of days 1, 2, 3, 4 or 5 of a cycle during the cycle.
- The duration of study drug in weeks will be $(\text{Date of the last dose} - \text{Date of the first dose} + 1) / 7$, including drug interruption days.
- Total dose (ug/kg) of study drug is the summarization of all the actual doses received during study. Actual dose (ug/kg) is calculated using $\text{planned dose (ug/kg)} \times (\text{actual volume(ml)}/\text{planned volume(ml)})$.
- Received dose as percentage of planned starting dose (%) = $\text{total dose (ug/kg)} / (\text{number of cycles} \times 5 \text{ (day)} \times 9 \text{ (ug/kg/day)}) \times 100$.
- Number of subject weeks = summation over all subjects' exposure durations.

Subject data listings will be provided for all dosing records, and for the summary statistics calculated above.

Study drug interruption and dose reduction instructions for subjects who experience an E7777-related toxicity are presented in Table 1 per protocol amendment 6 section 9.4.1.5. The number of subjects with dose reductions and treatment interruption will be summarized by counts and percentages.

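### Protocol 9.4.1.5 orders a full dose after any toxicity delay resolved within 21 days, with no exception for the Table 1 row that restarts at 50% after dose-limiting Grade 3 capillary leak syndrome

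*Protocol*

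**What the plan says.** Protocol 9.4.1.5 sets dosing after toxicity in two places, a bulleted list (Dose Delays) and Table 1.

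- The list opens by allowing delays for toxicity: "Resumption of dosing will be according to the guidelines provided in" Table 1.
- It then caps the delay: "The maximum delay is 21 days before the day the next course is scheduled to start". Two sub-bullets follow: "A full dose will be given if toxicities are resolved within this 21-day period" and "A dose delay lasting > 21 days will lead to permanent discontinuation of treatment".
- The next main bullet makes two consecutive toxicity delays a trigger for a permanent 50% reduction. Only one such reduction is allowed, and a need for a further one ends treatment.
- The section's closing sentence again points to the table: "Study drug interruption and dose reduction instructions for subjects who experience an E7777-related toxicity are presented in" Table 1.
- In Table 1, Grade 3 CLS is split in two. If judged not dose-limiting, dosing restarts at full dose once the event is Grade 1 or less. If judged dose-limiting, the interruption is the same but the instruction is "Resume at 50% dose".

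SAP 6.7.1, in describing exposure summaries, also says that the interruption and reduction instructions "are presented in Table 1 per protocol amendment 6 section 9.4.1.5".

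**The concern.** The full-dose sub-bullet is specific and mandatory. Nothing in it defers to Table 1 or to the two-delay rule. The general reference to Table 1 comes earlier, and no statement says which text prevails where they differ.

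The subject at issue has had CLS severe enough for admission for acute treatment, which section 9.1.2 classes as a dose-limiting toxicity. Section 7.3.1 names CLS as one of the two most notable adverse events of the parent product. An investigator who applied the sub-bullet literally would re-expose that subject to twice the dose in Table 1 and could cite protocol text for doing so. What is at stake is subject safety. The dose-reduction counts and received-dose percentage in SAP 6.7.1 could also shift, but that is secondary.

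**Working it through.** The plan states no statistical figure on this point, so the check is a comparison of texts plus simple arithmetic.

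**1. How many Table 1 rows are affected.** Table 1 has 11 toxicity rows:

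- 4 stop treatment permanently: Grade 4 CLS; Grade 4 or recurrent Grade 3 infusion reaction; visual loss; Grade 4 nonhematologic toxicity.
- 1 continues without interruption: first Grade 2 or 3 infusion reaction.
- 6 interrupt and resume.

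4 + 1 + 6 = 11. Of the 6, 5 resume at full dose and agree with the sub-bullet. One, dose-limiting Grade 3 CLS, resumes at 50% and does not.

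**2. The rules side by side.**

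| Situation | Sub-bullet read alone | Other text in 9.4.1.5 |
|---|---|---|
| Dose-limiting Grade 3 CLS, delay resolved within 21 days | Full dose | Table 1: 50% |
| Second consecutive toxicity delay, resolved within 21 days | Full dose | Two-delay bullet: permanent 50% |
| Delay of more than 21 days | Does not apply | Permanent discontinuation |

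The first two rows contradict each other across the columns. The third does not.

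**3. Size of the difference, Main Study.** Section 9.4.4 gives 9 µg/kg/day. Section 9.4.1 gives "5 consecutive days in every 21-day cycle".

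- Daily dose: 9 versus 9 × 0.5 = 4.5 µg/kg.
- Per course: 9 × 5 = 45 versus 4.5 × 5 = 22.5 µg/kg.
- Ratio: 45 / 22.5 = 2.

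In the SAP 6.7.1 formula, whose denominator is 5 × 9 = 45 µg/kg per cycle, a completed cycle at the two doses would count as 45/45 = 100% or 22.5/45 = 50%.

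**4. When the conflict arises.** This depends on how the maximum-delay bullet is read.

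- *Delay counted from the day the next course is due.* With a 21-day cycle that day is Day 22. A delay of 1 to 21 days means a restart on Day 22 + 1 = 23 to Day 22 + 21 = 43. CLS beginning on Day 1 has 22 − 1 = 21 days to resolve before the next course is due, and on Day 5, 22 − 5 = 17 days. If it resolves in that time, no course is delayed and Table 1 alone governs. The documents do not limit CLS onset to dosing days, so the margin can be shorter.
- *The 21 days preceding the next course.* The conflict then moves to events that resolve within the cycle.

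Footnote j of the Schedule of Assessments allows ±1 day for the start of a cycle from Cycle 3 onward, so a Day 23 start need not be a delay there. The edges of the window are therefore uncertain. On either reading there is a set of cases in which the full-dose sentence contradicts the 50% row.

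**The case against.** The strongest reply is that the section already says which rule governs. Its first bullet sends resumption to Table 1, and its closing sentence sends dose reduction there again. In context, the sub-bullet may describe only what a delay does by itself: one resolved delay causes no reduction, a longer one ends treatment, and two in a row halve the dose. Reductions tied to a particular toxicity would then belong to Table 1. That reading reconciles the section. A physician who has classed a Grade 3 event as dose-limiting is also looking at the row that prints the 50% instruction.

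This settles the intent: 50%. SAP 6.7.1 adds little, since it cites Table 1 for exposure summaries and does not direct dosing. Showing the intent does not remove the contrary instruction, which stays mandatory and unqualified.

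A reader might also infer more than the documents support:

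- *That the rules clash in every case of dose-limiting CLS.* On the reading that counts delay from the due day, an event that resolves before the next course is due delays nothing, and Table 1 stands alone.
- *That the conflict occupies a fixed Day 23 to 43 window.* That assumes one reading of an awkward bullet and ignores the start window from Cycle 3.
- *That subjects were over-dosed or the response rate was affected.* The documents give no frequency and show no such event.

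**Conclusion.** The text is wrong as written, in a narrow case. When dose-limiting Grade 3 CLS causes a dose delay that resolves within the allowed 21 days, the sub-bullet gives 9 µg/kg/day in the Main Study and Table 1 gives 4.5. The sub-bullet likewise lacks an exception for the two-consecutive-delays rule. The 50% dose is evidently intended, so this is a contradictory instruction left beside the correct one, not a missing rule.

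The conclusion assumes only that the sub-bullet means what it says. The exact calendar limits remain open, and the number of subjects concerned cannot be stated. Sample size, alpha and the primary response-rate analysis are not in question. It should be corrected because the error it permits doubles the restart dose after a dose-limiting event and the correction is small.

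**What to change.** Keep the sub-bullet and qualify it, so that it reads: "A full dose will be given if toxicities are resolved within this 21-day period", *unless Table 1 or the two-consecutive-delays rule requires a 50% dose or discontinuation.*

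Full dose stays the default for holds that Table 1 does not fully cover, such as the low-albumin hold in 9.4.1.3 or Grade 3 liver enzyme elevation, which its Grade 3 nonhematologic row excludes. The change should go no further. In particular, it should not bar re-escalation after every reduction: the protocol attaches that bar to the two-delay reduction, and Table 1 does not state it for the CLS reduction.

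The cost is one sentence in a protocol amendment. Because it concerns subject safety, section 11.1 calls for submission to the authorities and ethics committee approval. Table 1, the visit schedule and the SAP need no change.

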**Table 1 Dose Interruption and Modification During Treatment Period**

Toxicity	Dose Interruption	Dose Modification
Capillary leak syndrome a Grade 4	Discontinue study treatment permanently	N/A
Capillary leak syndrome Grade 3, 2. assessed as dose-limiting , e.g. severe symptoms requiring hospitalization for acute intervention	Interrupt dosing until resolved to ≤ Grade 1	Resume at 50% dose
Capillary leak syndrome Grade 3, - assessed as not dose-limiting , e.g. less severe symptoms leading to hospitalization for prophylactic treatment with fluids or diuretics	Interrupt dosing until resolved to ≤ Grade 1	Resume at full dose
Infusion reaction b Grade 4 or Recurrent infusion reaction Grade 3 that recurs despite premedication with systemic steroids	Discontinue study treatment permanently	N/A
Infusion reaction Grade 2 or 3, first occurrence	None	Continue at full dose, but add systemic steroid premedication
Recurrent infusion reaction Grade 2 that recurs despite premedication with systemic steroids	Interrupt dosing until resolved to ≤ Grade 1	Resume at full dose, but may add systemic steroid premedication f
Infusion related reaction c Grade 2 or 3	Interrupt dosing until resolved to ≤ Grade 1	Resume at full dose, but may add systemic steroid premedication f
Visual loss d	Discontinue study treatment permanently	N/A
Grade ≥ 3 hematological ≥ 7 days, or febrile neutropenia, or bleeding. Exception: Grade 3 lymphopenia e	Interrupt dosing until toxicity ≤ Grade 1, or until clinical symptoms are resolved	No change; Resume at full dose
Grade 3 nonhematologic toxicity except nausea, vomiting, or elevation of liver enzymes.	Interrupt dosing until toxicity ≤ Grade 1 or baseline	No change; Resume at full dose
Grade 4 nonhematologic toxicity other than, nausea, and vomiting.	Discontinue study treatment permanently	N/A

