**Table 1 Dose Interruption and Modification During Treatment Period**

Toxicity	Dose Interruption	Dose Modification

CLS = capillary leak syndrome, CTCAE = Common Terminology Criteria for Adverse Events, IRR = infusion-related reaction, N/A = not applicable.
 
a Refer to Section 9.1.2 for definition of capillary leak syndrome (CLS) and of DLT for CLS
 
b Infusion reactions are infusion related reactions that occur within 24 hr of E7777 administration; see Section 9.1.2 definitions
 
c Infusion related reactions can occur at any time during the treatment cycle
 
d Visual loss is defined as visual acuity impairment, color or shape distortion, or blurred vision
 
e These toxicities were observed for E7777 in a Phase 1 study and are expected toxicities.
 
f See Section 9.4.1.1 for detailed instructions on systemic steroid premedication
		

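### Table 1 gives conflicting instructions for two types of infusion reaction within 24 hours, because its footnotes nest one category inside the other and state no precedence

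*Protocol*

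**What the plan says.** Four rows of Protocol Table 1 deal with infusion events.

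- The row headed "Infusion reaction Grade 2 or 3, first occurrence" calls for no interruption, and its modification column reads "Continue at full dose, but add systemic steroid premedication".
- A second row covers a repeat event at the lower of those two grades, described as "Recurrent infusion reaction Grade 2 that recurs despite premedication with systemic steroids". Its interruption column tells the site to hold treatment until the event has settled to Grade 1 or lower, and its modification column reads "Resume at full dose, but may add systemic steroid premedication".
- A third row covers any Grade 4 event and also "Recurrent infusion reaction Grade 3 that recurs despite premedication with systemic steroids". Both lead to permanent discontinuation.
- The last row covers an infusion related reaction of Grade 2 or 3. Its interruption and modification wording is identical to that of the second row.

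The two labels are explained in the footnotes. Footnote b defines the narrower one: "Infusion reactions are infusion related reactions that occur within 24 hr of E7777 administration". The broader one is left open in time by footnote c: "Infusion related reactions can occur at any time during the treatment cycle". Footnote f, attached to the two optional-steroid entries, sends the reader to Section 9.4.1.1.

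Section 9.4.1.1 makes systemic steroids mandatory for the rest of Cycle 1 when a Grade 2 or 3 infusion reaction follows the first dose on Cycle 1 Day 1. For an infusion related reaction at any time in any cycle, it leaves them to the treating physician. The Main Study follows the same guidance as the Lead-In.

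**The concern.** Table 1 tells a site what to do next when a subject reacts to the drug. Section 7.3.1 names infusion reaction as one of the two most notable adverse events of ONTAK, so these rows matter for subject safety. If one event can be placed in two rows that disagree, two sites can follow the protocol and act differently.

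Some reported results depend on that action:

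- SAP Section 6.7.1 counts subjects with dose reductions and treatment interruption.
- SAP Section 6.7.2 tabulates TEAEs leading to drug interruption and to discontinuation.
- Under Protocol Section 9.4.1.5, two consecutive toxicity delays lead to a permanent 50% dose reduction, and a delay of more than 21 days ends treatment. The row used can feed these rules where an interruption becomes a delay.
- SAP Section 6.5.3.1 compares ORR between subjects who did and did not receive steroid medication. Membership of those groups can depend on whether steroid was treated as required or optional.

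**Working it through.** The documents give no figure to reproduce, and no arithmetic applies. The check is one of set membership: apply footnotes b and c to each infusion event within 24 hours, list the rows it meets, and compare the instructions.

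By footnote b, every infusion reaction is an infusion related reaction. By footnote c, the infusion related category covers the whole cycle, and the first 24 hours are not carved out. So a Grade 2 or 3 event within 24 hours always meets the general infusion related row, and may also meet a specific row.

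| Event within 24 hours | Specific row | General row | Result |
|---|---|---|---|
| Grade 2 or 3, first occurrence | No interruption; full dose; steroid added | Interrupt to Grade 1 or lower; full dose; steroid optional | Conflict on interruption; steroid required versus optional; dose level agrees |
| Grade 2, recurs despite steroids | Interrupt to Grade 1 or lower; full dose; steroid optional | Same wording | Two rows, no conflict |
| Grade 3, recurs despite steroids | Permanent discontinuation | Interrupt to Grade 1 or lower; full dose; steroid optional | Conflict on whether treatment continues |
| Grade 2 or 3, recurs without steroid premedication | None fits | Interrupt to Grade 1 or lower; full dose; steroid optional | One row only |
| Grade 4 | Permanent discontinuation | Does not apply (Grade 2 or 3 only) | One row only |

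Of these five event types, three meet two rows, and two of those three receive conflicting instructions. The fourth type can arise because Section 9.4.1.1 leaves steroids in later cycles to the physician's discretion.

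Two further comparisons do not depend on the overlap of rows.

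1. *Table 1 against Section 9.4.1.1.* The first-occurrence row tells the site to add steroid with no limit on cycle or day. Section 9.4.1.1 makes it mandatory only after a reaction to the Cycle 1 Day 1 dose. A first Grade 2 reaction within 24 hours of a Cycle 2 dose is therefore an unqualified addition in Table 1 and discretionary in Section 9.4.1.1.
2. *The recurrent Grade 2 row against itself.* Its toxicity column describes a reaction that recurred despite steroid premedication. Its modification column then offers to add steroid premedication.

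Neither Table 1, its footnotes nor the rest of Section 9.4.1.5 contains a tie-break. Usage elsewhere does not supply one. Section 9.4.1.3 speaks of acute infusion-related reactions in connection with slowing or stopping the infusion, so the term is not reserved for late onset. Section 9.1.2, to which footnote b refers, uses the CTCAE term for infusion related reaction when defining a serious infusion reaction.

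**The case against.** The strongest reply is that a specific row governs over a general one. Table 1 uses two labels with separate footnotes, Section 9.4.1.1 repeats the distinction, and Section 9.1.2 ties infusion reactions to the 24-hour window. If the general row governed the first 24 hours, the first-occurrence row would have no function and the recurrent Grade 2 row would be redundant. The discontinuation row names its event exactly, and Section 9.1.2 names the same event as dose-limiting in Cycle 1. This is the more natural reading, and it makes divergent handling less likely. It is still an inference: no precedence is printed. It also leaves untouched the mismatch with Section 9.4.1.1 and the wording of the recurrent Grade 2 row.

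A second reply is that Sections 9.4.1.3 and 9.4.1.4 already provide for slowing, stopping or withholding an infusion for listed acute signs, whichever row is used. That narrows the practical gap on interruption, but it does not say which Table 1 row governs later dosing.

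A third is that adding steroid satisfies both a required and an optional instruction. That is so for a site that adds it. A site that reads the entry as optional and does not add it would still depart from the first-occurrence row.

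A fourth is that the option in the recurrent Grade 2 row could refer, through footnote f, to the remaining treatment days or later cycles. That is possible, but the row does not say so.

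A reader might go further and infer that every Grade 2 or 3 reaction in the first 24 hours falls in two rows with opposite instructions. The documents do not support that. A reaction recurring without steroid premedication meets only the general row, a Grade 2 reaction recurring despite steroids gets identical instructions in both, and for a first occurrence the direct opposition is confined to the interruption column.

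**Conclusion.** Table 1 is internally inconsistent for two event types: a first Grade 2 or 3 reaction within 24 hours, and a Grade 3 reaction within 24 hours that recurs despite steroid premedication. The conclusion rests only on the wording of footnotes b and c and the absence of a stated precedence. The difference from Section 9.4.1.1 and the fault in the recurrent Grade 2 row stand whichever way the overlap is read.

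The size is limited. The documents give no frequency of these reactions, so the number of subjects affected cannot be computed, and different handling across sites is a risk drawn from the text, not a recorded event. The analyses exposed are the descriptive interruption, reduction and discontinuation summaries and, through steroid use, the grouping in the ORR sensitivity analysis. A reader might infer that the main efficacy result or the general adverse event rates are in doubt. They are not on this ground: the primary ORR method, the sample size, and TEAE incidence by preferred term and grade do not depend on the row chosen. The case for acting is that these are safety instructions and the correction is simple.

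**What to change.** The sponsor's clinicians should reconcile Table 1 and its footnotes b, c and f with Sections 9.4.1.1 and 9.1.2, so that each combination of grade and recurrence maps to a single instruction and the steroid wording agrees between the table and the text. The recurrent Grade 2 row should be corrected in the same revision. Which instruction applies to each event, and how the rows are to be separated, is for the sponsor's clinicians; this review takes no position on either.

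The cost is a protocol clarification or a memo to sites. No new data, change of sample size or change to the primary analysis is needed.
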